10.3.10. PMM Phenotypic Description

Categorical shift tables from baseline to Week 24 will be summarized, including marginal totals, for the 3 phenotypic questions. The table will include categories for withdrawn and missing. Percentages will not be presented for the withdrawn and missing rows, and the percentages presented will use the number of non-missing values as the denominator.

10.4. RELATIONSHIP OF ENDPOINTS

To assess the relationship of the primary endpoint to other efficacy endpoints, scatter plots will be generated for the changes from baseline in 12MWD at Week 12 and Week 24 versus changes from baseline for the secondary endpoint PROMIS T-score and the exploratory endpoints, 30 second sit to stand, MFIS (physical, cognitive, psychosocial and total), the 8 scales for SF-36 and BPI (pain severity and pain interference). The plots will identify treatment group and the visit week. The Pearson correlation coefficients for each treatment group at Week 12 and for Week 24 will also be presented in the footnote of the plots.

For PGIC muscle symptoms and PGIC fatigue symptoms a box plot of change from baseline in 12MWD will be presented for each response level and treatment group at Week 12 and at Week 24 separately. The plot will be repeated for the 2 PGIS symptoms with the response levels of improvement, no change and worsening from baseline.

11. ANALYSIS OF PHARMACOKINETIC ENDPOINTS

The mavodelpar concentrations will be evaluated using the PK set. mavodelpar concentrations will be summarized at each scheduled time point on Day 1 and Weeks 12 and 24 using descriptive statistics. For post-dose samples, only concentrations collected within a 10% window of the protocol specified post dose time point will be included. Similarly, pre-dose concentrations will only be included if the samples were taken prior to dosing on the day. The number of subjects with a BLQ value will also be tabulated.

Linear and log-linear individual concentration profile spaghetti plots against time will be produced for Day 1 and Weeks 12 and 24. All subjects will be displayed on the same plot and mutational genotype (m.3243A>G, m.8344A>G, mt deletion or Other) will be identified. The actual sampling time will be used on the x-axis with pre-dose fixed at zero for all subjects.

Linear and log-linear median concentration profile plots against time will be produced for Day 1 and Weeks 12 and 24. The nominal sampling time will be used on the x-axis. Lines will be included for all subjects and by mutational genotype.

A listing of all concentration data will be presented. The actual time post dose, deviation and percent deviation from nominal post dose time will also be listed for the post dose samples on Day 1 and Weeks 12 and 24. For all other visits the actual time relative to dose the sample was collected will be listed.

Concentration values will be presented to 3 significant figures.

12. ANALYSIS OF SAFETY DATA

All safety evaluations will be performed using the safety analysis set unless specified otherwise.

12.1. ADVERSE EVENTS

AEs will be coded using MedDRA version 23.1.

AEs will be considered treatment-emergent (TE) unless there is a clear indication that the event occurred prior to the first dose of study drug. AEs with missing start dates will be taken as TE unless the end date occurs before Day 1. If there is a partial start date, then the AE will be taken as TE unless suggested otherwise by the partial information provided and the end date. Events that occur after informed consent and prior to the first study dose are to be reported as pre-treatment AEs. Therefore, only TEAEs are to be reported on the adverse event eCRF page. Onset dates will be checked against the first dose date to ensure there is no conflict in this designation.

If an adverse event has a missing start date (where stop date is after the dosing date or missing) the date will be imputed as the dosing start date and for a missing start date (where stop date is before the start date of dosing) the date will be imputed as the day of informed consent and the event will be classified as a pre-treatment AE; for a missing stop date the TEAE will be considered as ongoing at the last visit date. If a partial date is recorded, the following convention will be used to assign the AE:

- If a start date is missing the day information and month/year is the same as the dosing start date then use the dose start date, else '01' will be used for the day; if a start date is missing the day/month and the year is the same as the dosing start date then use the dose start date, else January will be used for the start month.
- If a stop date is missing the day information and month/year is same as last study date then use last study date, else last day of the given month will be used for the stop day; if a stop date is missing the day/month and year is the same as last study date then use last study date, else December will be used for the stop month.

Only TEAEs will be included in the summary tables. Summaries will be generated for all TEAEs and for TEAEs that are emergent no more than 7 days after the last dose of study drug. The latter approach is to exclude any AEs reported by subjects when there is no likely systemic presence of mavodelpar – this is made even more possible by the encouragement of subjects to remain in the study if they discontinue study treatment prematurely. Those specific summaries generated for both all TEAEs and those not more than 7 days after the last dose are identified below; all other summaries will only be generated for all TEAEs.

An overall summary (for all TEAEs and those not more than 7 days after the last dose) will present the number and percentage of subjects with:

- any TEAE
- any TEAE considered as related to study drug (evaluated by the investigator as Possibly Related or Related)
- any TESAЕ
- any TESAЕ considered as related to study drug
- any AESI
- Maximum severity TEAE of mild, moderate or severe; i.e. a subject with TEAEs at different intensities will be summarized at the most severe intensity
- Maximum severity for TEAE considered as related to study drug
- any TEAE leading to study drug discontinuation
- any TEAE leading to death

The table will include the total number of TEAEs reported. The total number of unique terms within subjects will also be presented, counting each TEAE PT only once within each subject.

The number and percentage of subjects with TEAEs will be presented (for all TEAEs and those not more than 7 days after the last dose) by System Organ Class (SOC) and PT. Subjects with multiple TEAEs within a SOC or SOC/PT combination will be counted only once for that SOC or SOC/PT combination. Similar summaries will be presented for related TEAEs, AESI and TESAЕs.

In addition, the AESI of refraction disorders will be summarized by lower-level term. The lower-level term will identify the direction of diopter change.

SOC and PT summaries of TEAEs by maximum severity (mild, moderate or severe) will be presented.

All summaries will be ordered by descending frequency of total number of subjects within each SOC and then similarly by decreasing frequency of total number of subjects within each PT, in the mavodelpar treatment group. In cases of SOC or PTs with equal frequencies, AEs will be sorted alphabetically.

All AEs will be listed with their onset and end study days. AE duration (stop date/time – start date/time or [stop date – start time + 1] for AEs with no time information) will be included in the listing for those AEs no longer ongoing; where applicable imputed data will be used for the calculation of AE duration, but the original date/time information will be presented in the listing. For ongoing AEs the duration will be calculated using the

subject's last study date and will be presented prefixed by '>'. The listing will identify treatment emergent AEs, AESI and SAEs. TEAEs that occur more than 7 days after the last dose of study drug for those subjects who have discontinued treatment will also be identified.

A separate listing of TESAEs, TEAESI and TEAEs leading to study drug discontinuation will also be generated. If there are any deaths a listing will include the date of death and the adverse event(s) associated with death.

but will only include those subjects who satisfy the criteria for a specific parameter. The records satisfying the criteria will be identified on the listing. The criteria are:

Category	Parameter	Criteria
Chemistry	Creatine kinase (CK)	Normal baseline value and post $\geq 5 \times$ ULN $> \text{ULN}$ baseline value and post $\geq 5 \times$ baseline level
	Aldolase	Normal baseline value and post $> \text{ULN}$
	Troponin I	$> \text{ULN}$
	Potential Hy's Law (ALT, AST, total bilirubin and alkaline phosphatase)	ALT or AST $> 3 \times \text{ULN}$ and Total bilirubin $> 2 \times \text{ULN}$ and Alkaline Phosphatase $\leq 2 \times \text{ULN}$

An evaluation of Drug-Induced Serious Hepatotoxicity (eDISH) plot will be generated. The plot will include all post baseline data and will present ALT relative to the upper limit of normal (ULN) on the x-axis and total bilirubin relative to the ULN on the y-axis using a log scale for both axes. Reference lines for Hy's law thresholds, i.e., ALT = 3 x ULN and total bilirubin = 2 x ULN, will be added. The plot will identify treatment group and mutational group and separate plots will be done for on-treatment and off-treatment records.

A spaghetti plot for the changes from baseline in creatine kinase (CK referred to in the protocol as creatine phosphokinase [CPK]) over time will be presented. The actual sampling day will be used on the x-axis (baseline will be set to day 1). A solid line will be used to connect measurements; however, if the measurement was collected after the last dose of study drug plus one day, then a dotted line will be used. Treatment group will be identified on the plot. The plot will be repeated for aldolase and troponin I.

Individual CK, aldolase, ALT, AST and troponin I values relative to the ULN will be plotted over time (i.e., one plot per subject) and treatment group and mutation type will be identified. The actual sampling day will be used on the x-axis (baseline will be set to day 1). The day of last dose of study drug will be identified on the plot with a vertical reference line.

All individual central laboratory results will be listed. The listing will include change from baseline values and values relative to the ULN. The last on-treatment measurements and values outside the laboratory reference range will be identified.

Local laboratory results will not be summarized and will be listed separately from central laboratory results.

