- Frequency of re-testing can decrease to once a week or less if abnormalities stabilize or the study drug has been discontinued and the subject is asymptomatic.
- Obtain a more detailed history of symptoms and prior or concurrent diseases.
- Recheck history of concomitant drug use (including non-prescription medications and herbal and dietary supplement preparations), alcohol use, recreational drug use, and any special diets.
- Rule out acute viral hepatitis types A, B, C, D, and E; autoimmune or alcoholic hepatitis; Non-alcoholic steatohepatitis (NASH); hypoxic/ischemic hepatopathy; and biliary tract disease.
- Obtain a history of exposure to environmental chemical agents.
- Obtain additional tests to evaluate liver function, as appropriate (e.g., International normalized ratio (INR) or Prothrombin time (PT), direct bilirubin).
- Consider gastroenterology or hepatology consultations.

Discontinuation:

Discontinuation or interruption of study drug should be considered, in consultation with the Medical Monitor and Reneo CMO or designee where possible, if:

- ALT or AST > 8xULN.
- ALT or AST > 5xULN for more than 2 weeks.
- ALT or AST > 3xULN and total bilirubin > 2xULN or INR >1.5.
- ALT or AST > 3xULN with the appearance of fatigue, nausea, vomiting, right upper quadrant pain or tenderness, fever, rash, and/or eosinophilia (>5%).

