Unless stated otherwise, an on-treatment measurement will be any measurement collected (including scheduled and unscheduled visits) up to the date of last dose plus one day for safety endpoints and plus seven days for efficacy endpoints. Drug interruptions will not be considered, i.e., data will not be excluded during a drug interruption if the subject resumes study treatment.

In by-visit summary tables, the baseline will be summarized using all available data, but also for each visit using only the baseline data from subjects with available data at the visit; hence the mean change from baseline will equal the mean observed visit value – mean baseline value.

Throughout this document ‘change from baseline’ refers to the actual change from baseline (i.e., observed visit value – baseline value).

Summary tables will be split by treatment group (REN001 100 mg and placebo). Baseline summary tables (disposition, demography, baseline characteristics, medical history and prior medications) will also include an overall summary.

All data for randomized subjects, who receive at least one dose of study medication, will be listed. For screen failure subjects only disposition (including reason for screen failure), demographics and protocol deviations will be listed.

Data listings will be ordered by treatment group and subject. A subject’s mutational genotype (m.3243A>G, m.8344A>G, mt deletion or Other) will be identified on the listings. Data listings will present study days in addition to dates, where study day is derived as per SDTM guidelines i.e., study day is derived as (assessment date – first day of dosing +1) after the start of dosing and as (assessment date – first day of dosing) before the start of dosing. Hence, the first day of dosing will be identified as Study Day 1.

All statistical analyses will be performed using SAS® (Version 9.4 or higher, SAS Institute Inc., Cary, NC, USA).

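### The eDISH plots in SAP 12.2 show no per-subject peak across on- and off-treatment periods, so a bilirubin rise after stopping drug may fall in neither Hy's Law quadrant

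*SAP*

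**What the plan says.** SAP Section 12.2 describes the eDISH plot in a few sentences. On content: "The plot will include all post baseline data and will present ALT relative to the upper limit of normal (ULN) on the x-axis", with total bilirubin relative to ULN on the y-axis. The reference lines are "ALT = 3 x ULN and total bilirubin = 2 x ULN". On layout: "The plot will identify treatment group and mutational group and separate plots will be done for on-treatment and off-treatment records". No subject identifier is specified for this plot, although the laboratory box plots in the same section do carry one for outliers. No per-subject maximum is mentioned.

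SAP Section 8.2 defines on-treatment as "up to the date of last dose plus one day for safety endpoints". It adds that "data will not be excluded during a drug interruption if the subject resumes study treatment".

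Other liver outputs in SAP 12.2:
- a count of subjects meeting the potential Hy's Law criteria, based on on-treatment values;
- per-subject time plots of CK, aldolase, ALT, AST and troponin I, without bilirubin;
- a listing of all central laboratory results, with values relative to ULN.

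Protocol Section 3.7.2 lists the circumstances in which "Discontinuation or interruption of study drug should be considered". Some rest on ALT or AST alone (above 8xULN, or above 5xULN for more than 2 weeks). Others combine ALT or AST with bilirubin, INR or symptoms.

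**The concern.** The eDISH figure is the plan's visual screen, by arm, for serious drug-induced liver injury. If points are single samples, one reaches the upper-right quadrant only when the same sample has both ALT above 3xULN and bilirubin above 2xULN. The sequence of interest is a rise in ALT, drug stopped, then a rise in bilirubin while ALT is falling. That sequence can leave one dot at the lower right of the on-treatment figure and another at the upper left of the off-treatment figure.

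With no subject identifier specified, a reader could not match the two dots. The protocol expects ALT and AST rises of muscle origin in PMM, so a lower-right dot would not stand out by itself. At stake is whether a delayed case is visible in the summary outputs or only by reading listings.

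**Working it through.** The plan states no figure to reproduce here. The check applies the SAP's own rules to assumed laboratory courses.

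**Inputs**
- Quadrant: ALT > 3xULN and total bilirubin > 2xULN (SAP 12.2).
- On-treatment: day relative to last dose ≤ +1 (SAP 8.2).
- Plotting unit: not stated. The SAP's reference to records makes one point per sample the natural reading, so both that and a within-period maximum are tested.
- Laboratory values: assumed, to show the mechanism only.

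**Simple example.** Last-dose sample (6.0, 1.2): 6.0 > 3 but 1.2 ≤ 2, so outside. Day +7 sample (2.5, 2.4): 2.5 ≤ 3, so outside. Each period holds one sample, so within-period maxima give the same result. Peaks over both periods: (6.0, 2.4), with 6.0 > 3 and 2.4 > 2, so inside.

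**Five courses.** Records are (day, ALT/ULN, bilirubin/ULN). In every course ALT peaks on drug and bilirubin peaks after the last dose.

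| Course | Records | Single records, split | Single records, unsplit | Within-period maxima, split | Subject maxima, unsplit |
|---|---|---|---|---|---|
| A | (-14, 6, 1.0), (0, 8, 1.5), (7, 2.8, 2.5), (14, 1.5, 3.0) | neither | no | neither | yes |
| B | (-14, 6, 1.0), (0, 8, 1.5), (7, 5, 3.0), (14, 2, 2.2) | off | yes | off | yes |
| C | (-7, 5, 1.2), (0, 8, 2.3), (7, 2.5, 4.0) | on | yes | on | yes |
| D | (0, 8, 1.5), (1, 7, 3.0), (10, 2, 1.5) | on | yes | on | yes |
| E | (0, 8, 1.5), (4, 3.6, 1.9), (10, 2.5, 2.6) | neither | no | off | yes |
| Shown | | 3 of 5 | 3 of 5 | 4 of 5 | 5 of 5 |

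Reading across:
- A and E are missed at record level because no single sample exceeds both lines. B, C and D are shown because one does. In D that sample is on day +1, which still counts as on-treatment.
- Dropping the split while keeping single records changes nothing: A and E are still missed.
- With within-period maxima E is recovered, but A is not: its maxima are (8, 1.5) on drug and (2.8, 3.0) off drug.
- Only maxima taken over both periods together show all five.

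**The tabulated count.** In A and E every on-treatment bilirubin is at or below 2xULN (1.0 and 1.5 in A; 1.5 in E), so the on-treatment potential Hy's Law count does not register either subject.

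**The case against.** The strongest objections are these.

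1. **The documents' own concept is concurrency.** Protocol Section 7.1.1.6.1 describes a Hy's Law case as transaminase and bilirubin abnormalities present together without another known cause. Pairing values by sample fits that, and neither document says an eDISH plot must show peak against peak. This stands. The case for an extra figure rests on what the specified plots can miss, not on an outside convention.

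2. **Other safeguards exist.** The same protocol section treats Hy's Law cases as SAEs, without a 3xULN threshold. SAEs are collected up to 30 days after last dose (Protocol 7.1.1.9), and treatment-emergent SAEs are tabulated and listed. The day +7 sample in the simple example, with both values abnormal, could qualify. It would also show above the bilirubin line in the off-treatment plot. This stands and limits the severity. SAE reporting does depend on the investigator recognising the pattern, and the listing marks values outside the reference range but not such a pair.

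3. **Close observation makes a joint sample more likely.** Protocol 3.7.2 has ALT, AST, ALP and bilirubin repeated together two or three times weekly, and interruption or discontinuation is only to be considered. This is fair: frequent joint sampling lowers the chance of courses like A and E without excluding them.

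4. **The plotting unit is inferred.** Table and figure layouts are in separate shells (SAP 2.1). True, but course A and the simple example are missed under either unit.

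A reader might also infer more than the documents support: that any subject whose ALT peaks on drug and whose bilirubin peaks after stopping never appears, and that the split is the cause. Courses B, C and D contradict the first. The unsplit record-level result contradicts the second. Samples during an interruption with resumed dosing also count as on-treatment.

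**Conclusion.** The point holds in a limited form. A subject with ALT above 3xULN on drug, and bilirubin above 2xULN only later, may be absent from the Hy's Law quadrant of both planned plots if no single record exceeds both thresholds. The on-treatment-only count would miss the same subject, and the per-subject time plots would not show the bilirubin course.

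Severity is minor. This is a gap in display and summary: no data are lost, no estimate or test is affected, and SAE reporting and the listings remain. The conclusion rests on the SAP text as written, with no subject-level maximum across periods added in the shells. The laboratory courses are assumed, so 2 of 5 missed at record level shows the mechanism and is not a rate. The documents give no basis for estimating how often this would happen.

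**What to change.** Add one eDISH figure by arm to SAP 12.2:
- one point per subject: maximum post-baseline ALT/ULN against maximum post-baseline total bilirubin/ULN, over on- and off-treatment records combined;
- subject ID on the points, and a mark for whether each peak was on or off drug;
- if wanted, a time window between the two peaks, stated before unblinding.

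Keep the existing split plots. Merging them without moving to subject maxima would not close the gap.

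The cost is one more programmed figure from central laboratory data already collected. The downside is that non-concurrent peaks can put an unrelated pair in the quadrant, for example a muscle-origin ALT rise and a raised bilirubin from Gilbert's syndrome, which the exclusion criteria can admit. Each such point should be checked against that subject's listing, and a pre-stated window would reduce their number. Local laboratory results are only listed under SAP 12.2, so the figure would not include off-drug retests done locally.

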12.3. DUAL ENERGY X-RAY ABSORPTIOMETRY (DXA) SCAN

Observed, change from baseline values and percent changes from baseline values for the DXA endpoints will be summarized for the DXA ScAS. The summary will be presented overall within the treatment group and by sex and menopausal status (i.e., men, pre-menopausal women and post-menopausal women).

A box and whisker plot will be presented for each of the parameters measuring the total spine and the 2 hip regions (total and femoral neck), for the DXA CScAS. The whiskers will display the 5th and 95th percentiles and outliers will be identified on the plot with subject ID. The plot will present the 2 visits alongside one another for each treatment group. The plot will be repeated by sex and menopausal status.

For the DXA CScAS, the study day of the follow-up DXA scan will be summarized using descriptive statistics. In addition, the number and percentage of subjects will be presented for the following relating to when they have their scan:

- whilst on treatment in REN001-201 (within 7 days of their last dose) and have not yet transitioned to the mavodelpar open-label study
- after discontinuing treatment in REN001-201, but having transitioned to the mavodelpar open-label study
- after discontinuing treatment in REN001-201 (> 7 days after their last dose) and not transitioned to the mavodelpar open-label study

12.4. VITAL SIGNS

Observed and change from baseline values will be summarized by visit and for the last on-treatment measurement using descriptive statistics.

Box plots of change from baseline by visit and treatment group will be presented for on-treatment measurements. The whiskers will display the 5th and 95th percentiles and outliers will be identified on the plot with subject ID. The number of observations contributing to each visit box plot will be included.

The number and percentage of subjects with an increase or decrease from baseline in on-treatment systolic blood pressure of <10 mmHg, ≥10 to <20mmHg, ≥20 to <30 mmHg or ≥30 mmHg will be summarized by visit. The denominator for percentages will be the number of subjects still on-treatment. This summary will be repeated for diastolic blood pressure using the following categories <5 mmHg, ≥5 to <10 mmHg, ≥10 to <15 mmHg, ≥15 to <20 mmHg, ≥20 to <25 mmHg or ≥25 mmHg.

Observed and change from baseline values will be listed. The listing will identify the increase or decrease from baseline categories detailed above for systolic and diastolic blood pressure. The last on-treatment measurements will be identified.

